5.1.4 Visit 5 (Treatment Exit)

Subjects will return to the clinical site 14-30 days after the seventh study cycle for exit from the study (Visit 5; Treatment Exit Visit). The following study activities will occur at this visit. In addition, these procedures should also be performed any time a subject discontinues the study prematurely.

- Vital signs (weight and blood pressure only)
- Perform physical examination (heart, lungs, and abdomen, and a breast exam at the discretion of the Investigator)
- Gynecological examination, including assessment of the vulva, vaginal wall, cervix, adnexae, and uterus. Wet mount for monilia, BV, and trichomonas will be performed only for symptomatic women.
- Perform chlamydia and gonorrhea tests only if the subject indicates that she has changed sexual partners or is symptomatic. If, according to the subject, her partner has been diagnosed or is being treated, she should be assessed per clinical site standard.
- CBC diff and chemistry panels to be sent to central laboratory for analysis
- Urine pregnancy test (if the test is positive and the pregnancy is deemed to be ontreatment, the subject should not be discontinued from the study but should have pregnancy assessments)
- Serum quantitative β-hCG pregnancy test
- Dipstick urinalysis (only to be performed if the subject presents to the center with urinary symptoms)
- Urine culture
- Administer questionnaires to assess subject satisfaction with study drug, sexual satisfaction, and pregnancy intendedness
- Review eDiary data report for completeness and accuracy
- Review study drug use adherence data
- Review backup contraception use and sexual activity
- Collect unused study drug and wrappers, and record drug accountability information
- Record concomitant medications (including any herbal or natural supplements)
- Record AEs

- Discuss post-study contraception with the subject
- For subjects who are discontinuing early from the study, the clinical site personnel should provide counseling about alternative methods of birth control and referral, as applicable

Investigators will note the presence or absence of vulvar, vaginal, or cervical findings (as defined in Section 5.4.3), including epithelial disruption, or areas of obvious erythema; these will be assessed as either not present, mild, moderate, or severe; the presence or absence of bleeding, petechiae, or sloughing will also be recorded on the gynecological exam eCRF and reported as an AE if considered by the Investigator to be a clinically significant change from baseline, defined as an at least one level increase in severity of the finding from baseline.

eDiary data reports will be reviewed to ensure that they do not contain any reported signs or symptoms related to drug use. If a sign or symptom is reported in the subject diary that warrants follow-up, the subject may be contacted for further information as necessary and may be asked to return to the clinical site for evaluation and/or treatment.

5.1.5 Contact Between Visits

Subjects will be contacted by telephone by the clinical site staff between Visits 3 and 4. All such contacts and attempts should be documented in the subject's source file. Between-visit contact is to include the following assessments:

- Record AEs
- Record concomitant medications (including any herbal or natural supplements)
- Review eDiary data reports for completeness and accuracy, and assess the need for subject re-training in eDiary use
- Review study drug adherence data
- Review backup contraception use and sexual activity
- Confirm subject has sufficient supply of study drug
- Identify any other issues; plan an unscheduled visit, if necessary
- Confirm subject contact information

5.1.6 Unscheduled Safety Visits

In the event that the subject reports any significant gynecological symptoms or any symptoms indicative of a possible UTI, she will be asked to contact the clinical site for evaluation. During unscheduled safety visits, the Investigator may perform a gynecological exam and appropriate laboratory tests and provide appropriate treatment as necessary. Subjects should be discouraged from any self-medication with vaginal products; rather, they should visit the clinical site for assessment and treatment. Similarly, subjects should be discouraged, but not prohibited, from seeking treatment for suspected UTIs or other vaginal infections at facilities other than the clinical site.

Based on the results of the gynecological exam and laboratory tests, if the Investigator determines that the subject should be discontinued, the Treatment Exit procedures (as detailed in Section 5.1.4) will be performed and the subject will be discontinued from the study. In addition, if at any time during the study a subject misses her period or suspects that she may be pregnant, she should call the clinical site to schedule a urine pregnancy test.

5.2 Emergency Contraception

In the event a subject engages in vaginal intercourse but believes that the study drug was not used properly or if she feels she is at risk for pregnancy for any other reason, she is eligible to request a prescription for EC or obtain her own as OTC. The individual clinical sites will provide EC in accordance with the standard of care of the clinical site. Any time EC use occurs, the date of usage as well as the reason for usage should be recorded as a concomitant medication in the source and the EDC system as well as the eDiary.

5.3 **Pre-Trial and Concomitant Medications**

At the Screening Visit and Enrollment Visit, the study subjects will be asked to report medications and health products that were taken at the time of screening and prior to enrollment, including any herbal or natural supplements, over the past six months. The subject's contraceptive use within the past year will also be recorded at these study visits.

The use of concomitant medications and health products will also be queried in the eDiary, at Visits 2-5 and during the between-visit contact. If vaginal symptoms are present, the subject should visit the clinical site for evaluation and treatment as indicated. Subjects should be instructed to abstain from any vaginal self-medication. All medications and health products taken by the participant during the course of the study, including all vaginal preparations and any medication given for the treatment of any AE must be recorded in the EDC system.

Subjects should be encouraged not to douche during the study; however, if douching does occur, the subject should wait to douche until at least six hours after the last act of intercourse and should record the product used as a concomitant medication in the eDiary. Similarly, subjects should be advised not to use any lubricants or vaginal preparations before or during intercourse. If use does occur, it should be recorded in the eDiary and as a concomitant medication.

5.4 Adverse Events

5.4.1 Collection of Adverse Events

It is the responsibility of the Investigator to collect all AEs (both serious and non-serious) derived by spontaneous, unsolicited reports of subjects, by observation, and by routine open questionings, e.g., "How have you felt since I last saw you?"

5.4.2 Definitions

For the purposes of this study, an AE is any unfavorable and unintended sign (including abnormal laboratory finding), symptom, or disease temporally associated with the use of the study drug, whether or not it is considered related.

All AEs, including intercurrent illnesses, occurring during the study will be documented in the EDC system. Illnesses that existed before entry into the study will not be considered AEs unless they worsen during the treatment period. All AEs, regardless of the source of identification (e.g., physical examination, laboratory assessment, reported by subject), must be documented.

Pre-existing conditions will be recorded in the EDC system on the appropriate page (e.g., Medical History)

AE data should be collected from enrollment until Visit 5 (14-30 days after the seventh study cycle) or early termination from the study. Those events that occur between the Screening Visit and enrollment will be analyzed as medical history. A treatment-emergent AE (TEAE) will be defined as an AE that begins or that worsens in severity after at least one dose of study drug has been administered. All AEs considered at least possibly related to study drug will be followed until resolution or, for chronic conditions, until deemed stable.

5.4.3 Assessment of Adverse Events

Each AE will be assessed by the Investigator for seriousness, intensity, and causality using the following definitions:

Seriousness

A serious AE (SAE) is defined as any untoward medical occurrence that at any dose:

- Results in death.
- Is life-threatening; this means that the patient is at risk of death at the time of the event; it does not mean that the event hypothetically might have caused death if it were more severe.
- Requires inpatient hospitalization or prolongation of existing hospitalization.
- Results in persistent or significant disability or incapacity.
- Is a congenital anomaly or birth defect.
- Is an important medical event(s) that may not be immediately life-threatening or result in death or hospitalization but that may jeopardize the patient or require intervention to prevent the above outcomes. Examples of such events are intensive treatment in an emergency room or at home for allergic bronchospasm; blood dyscrasias or convulsions that do not result in hospitalization; or development of drug dependency or drug abuse.

Medical and scientific judgment should be exercised in deciding whether a case is serious and whether expedited reporting is appropriate.

Intensity

Investigators should assess the severity of AEs according to Common Terminology Criteria for Adverse Events (CTCAE) version 4.03. In general, CTCAE severity grades are:

• Grade 1: Mild; asymptomatic or mild symptoms; clinical or diagnostic observations only; intervention not indicated

- Grade 2: Moderate; minimal, local or noninvasive intervention indicated; limiting ageappropriate instrumental Activities of Daily Living (ADL) (Instrumental ADL refer to preparing meals, shopping for groceries or clothes, using the telephone, managing money, etc.)
- Grade 3: Severe or medically significant but not immediately life-threatening; hospitalization or prolongation of hospitalization indicated; disabling; limiting self-care ADL (Self-care ADL refer to bathing, dressing and undressing, feeding self, using the toilet, taking medications, and not bedridden.)
- Grade 4: Life-threatening consequences; urgent intervention indicated
- Grade 5: Death related to AE

Causality

The Investigator will assess the causality/relationship between the study drug and the AE and record that assessment in the EDC system. The most likely cause of an AE (e.g., concomitant disease, concomitant medication, other) will be indicated in the EDC system with details of the concomitant disease or medication or other cause.

The causal relationship of the AE to study drug will be described per World Health Organization (WHO) Uppsala Monitoring Centre (UMC) causality categories¹⁵:

- Certain/Definite:
 - Event or laboratory test abnormality, with plausible time relationship to drug intake
 - Cannot be explained by disease or other drugs
 - Response to withdrawal plausible (pharmacologically, pathologically)
 - Event definitive pharmacologically or phenomenologically (i.e., an objective and specific medical disorder or a recognized pharmacological phenomenon)
 - Rechallenge satisfactory
- Probable/Likely:
 - Event or laboratory test abnormality, with plausible time relationship to drug intake
 - Unlikely to be attributed to disease or other drugs
 - Response to withdrawal clinically reasonable
 - Rechallenge not required
- Possible:
 - Event or laboratory test abnormality, with plausible time relationship to drug intake
 - Could also be explained by disease or other drugs
 - \circ $\,$ Information on drug withdrawal may be lacking or unclear $\,$
- Unlikely:
 - Event or laboratory test abnormality, with a time to drug intake that makes a relationship improbable (but not impossible)

- Disease or other drugs provide plausible explanations
- Not assessable:
 - Report suggesting an adverse reaction
 - Cannot be judged because information is insufficient or contradictory
 - Data cannot be supplemented or verified

Genitourinary Side Effects

Genitourinary (GU) side effects (including vaginal burning, vaginal itching, vaginal pain, and other unexpected vaginal symptoms) will be collected in the eDiary each time the study drug is used and will be recorded at AEs. Subjects will note the time of drug administration, time of sexual intercourse and if they had any side effect (including severity, duration, and resolution).

Unexpected vaginal bleeding or spotting will be recorded as AEs; however, expected menstrual-related bleeding and/or spotting will not.

Vulvar, Vaginal, or Cervical Side Effects

An adaptation of the Division of AIDS (DAIDS) Table for Grading the Severity of Adult and Pediatric Adverse Events, Version 2.0, Addendum 1 – Female Genital Grading Table for Use in Microbicide Studies will be used by the investigator to grade changes from baseline in vulvar, vaginal or cervical findings noted during the gynecologic exam and determine if they are considered significant, as defined as at least one grade increase from baseline. These should be reported as AEs. The Female Genital Grading Table for Use in Microbicide Studies was developed for use in protocols involving topical application of products to the female genital tract. Although developed specifically for microbicide studies, it is applicable to other protocols as well to ensure data consistency across sites.

Parameter	Grade 0	Grade 1	Grade 2	Grade 3
	Normal	Mild	Moderate	Severe
Epithelial	None	Blisters,	Blisters,	Severe epithelial
disruption		ulcerations,	ulcerations, large	disruption with
		superficial	disruptions –	hospitalization
		disruptions with	treatment	indicated
		minimal impact	indicated	
		on life – no		
		treatment needed		
Erythema	None	Erythema	Erythema	Severe erythema
		covering <50%	covering ≥50%	with
		of surface	of surface	hospitalization
				indicated
Parameter	Grade 0	Grade 1		
Bleeding	None	Present		
Petechiae	None	Present		
Sloughing	None	Present		

Table 3: Vulvar, Vaginal, or Cervical Individual Signs/Symptoms Grading Table

Recording Adverse Events

AE reporting will extend from enrollment until Visit 5 (14-30 days after the seventh study cycle). AEs occurring after Visit 5 should be reported to PAREXEL by the Investigator if the Investigator considers there is a causal relationship with the study drug.

All AEs, regardless of the relationship to study drug, will be recorded in the EDC system.

All AE reports should contain a brief description of the event, date and time of onset, date and time of resolution, intensity, treatment required, relationship to study drug, action taken with the study drug, outcome, and whether the event is classified as serious.

AEs reported as ongoing at the last study visit will be listed as ongoing as of the last study date, and time of resolution will be marked as Not Applicable.

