- i. Chlamydia and gonorrhea assessments to be performed at Visits 3, 4, and 5 only if the subject indicates that she has changed sexual partners or is symptomatic. If the subject reports that her partner has been diagnosed or is being treated, she should be assessed/treated as per clinical site standard.
- j. In addition to the urine culture at Screening and Visit 5, subjects will be instructed to contact the clinical site to schedule a dipstick urinalysis and possibly a urine culture any time they suspect they may have a UTI.
- k. If dipstick urinalysis is 1+ for analytes of blood, leukocyte esterase, protein or nitrites, the urine should be sent for urine culture and microscopic urinalysis.
- 1. Only to be performed if the subject presents to the clinical site with urinary symptoms. Dipstick urinalysis should be performed at any visit where a subject presents to the center with urinary symptoms.
- m. A urine pregnancy test should be administered any time a subject misses her period or suspects pregnancy. If a subject reports a positive home pregnancy test, a serum β-hCG should be performed.
- n. Subjects will record in their eDiary dates/times of gel use, dates/times of sexual activity, vaginal bleeding, and use of back-up contraception (including reasons for back-up contraception, if applicable). Additionally, subjects will record gel-related genitourinary side effects (vaginal itching, burning, or pain) and assess them as mild, moderate, or severe; these side effects and non-menstrual cycle vaginal spotting/bleeding will be analyzed as AEs. At each visit, Amphora and eDiary compliance data will be reviewed and subjects assessed for re-education. Between visits, sites and subjects will receive alerts if a subject has missed eDiary entries. Sites will record documentation of contact with the subject around eDiary compliance.
- o. Provide instructions on how to use the study drug at Enrollment Visit.
- p. Between-visit telephone contact is to include assessment of AEs, concomitant medications, sexual activity, use of backup contraception, compliance with use of the study drug and eDiary, need for an unscheduled visit, and confirmation of contact information.
- q. Includes confirmation of subject contact information. At the Enrollment Visit and each subsequent study visit/contact, the subject should be reminded to not have intercourse, use the study drug, or place anything in the vagina within 24 hours of the next scheduled visit to the clinical site.

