#### 4.7.1.2 Definition of Cycle

The cycle number will be derived from the eCRF menses start dates as follows:

Cycle 0 = date of enrollment through date before 1st menses started after enrollment (Note: this cycle includes cases where menses started on the day of enrollment)

Cycle 1 = date 1st menses started after enrollment through date before 2nd menses started after enrollment

Cycle 2 = date 2nd menses started after enrollment through date before 3rd menses started after enrollment

Cycle 3 = date 3rd menses started after enrollment through date before 4th menses started after enrollment

Cycle 4 = date 4th menses started after enrollment through date before 5th menses started after enrollment

Cycle 5 = date 5th menses started after enrollment through date before 6th menses started after enrollment

Cycle 6 = date 6th menses started after enrollment through date before 7th menses started after enrollment

Cycle 7 = date 7th menses started after enrollment through date before 8th menses started after enrollment

Cycle 8 = date 8th menses started after enrollment through date before 9th menses started after enrollment

If the subject became pregnant and the pregnancy adjudication committee estimated the date of conception, but the subject has no diary for the cycle that contains the estimated date of conception, then the pregnancy will be assigned to day 14 of the cycle. If partial start/end dates occur, then it will be assumed that the cycles were equal length to determine the imputed start/end dates of the cycle. If estimated date of conception could not be provided by the pregnancy adjudication committee due to insufficient information, then pregnancy will be assigned day 14 of the first potentially evaluable cycle after enrollment unless there is documentation to show the pregnancy occurred in a later cycle.

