#### **4.8.6 Gynecological Examination**

For gynecological examinations, each body system will be categorized as normal or abnormal. Gynecological examination changes from baseline will be categorized as improved, no change, or worsened for each body system. The number and percentage of subjects in each category of change will be given at each visit and final evaluation and body system.

An adaptation of *the Division of AIDS (DAIDS) Table for Grading the Severity of Adult and Pediatric Adverse Events, Version 2.0, Addendum 1 – Female Genital Grading Table for Use in Microbicide Studies* will be used by the investigator to grade changes from baseline in vulvar, vaginal or cervical findings noted during the gynecologic exam and determine if they are considered significant, as defined as at least one grade increase from baseline (see appendix 5.1).

Vulvar, vaginal, and cervical findings will be summarized by visit and final evaluation. The number and percentage of subjects and events for each grade will be presented.

Unscheduled visits will be grouped with the associated visit (e.g., visit 3.1 will be included with visit 3).

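### The menstrual-bleeding exemption in Protocol 5.4.3 is not carried into the Table 3 bleeding grade, the visit AE rules or SAP 4.8.6

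*Protocol*

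**What the plan says.** Two adjacent parts of Protocol 5.4.3 deal with bleeding.

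- **Genitourinary Side Effects.** "Unexpected vaginal bleeding or spotting will be recorded as AEs; however, expected menstrual-related bleeding and/or spotting will not". Table 1 footnote n says the same of eDiary data: "non-menstrual cycle vaginal spotting/bleeding will be analyzed as AEs".
- **Vulvar, Vaginal, or Cervical Side Effects.** The Investigator grades examination findings against baseline using Table 3, to "determine if they are considered significant, as defined as at least one grade increase from baseline. These should be reported as AEs". The bleeding row has two levels: "Bleeding None Present". SAP 5.1 repeats the table unchanged.

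The visit instructions restate the second rule. In Protocol 5.1.4, "the presence or absence of bleeding, petechiae, or sloughing will also be recorded on the gynecological exam eCRF and reported as an AE" is followed by the condition that the Investigator considers the change clinically significant, which is then defined as a rise of at least one level. Protocol 5.1.3 uses the same condition and definition for Visits 3 and 4. Table 1 footnote g also refers to the Investigator's judgement, without the one-level definition.

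On reporting, SAP 4.8.6 states: "Vulvar, vaginal, and cervical findings will be summarized by visit and final evaluation", with subjects and events counted for each grade. The output is Table 14.3.5.9. No menstrual exclusion is given.

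On timing, Visits 3 and 4 are tied to a cycle number, not to a day of the cycle (Protocol 4 and 5.1.3). Only the Screening Visit text (Protocol 5.1.1) mentions menstruation as a reason to spread procedures over several days. Baseline is the last measurement on or before enrollment (SAP 4.2), normally the Visit 2 examination. The SAP foresees enrollment at the onset of menses: in its definition of Cycle 0, "this cycle includes cases where menses started on the day of enrollment".

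**The concern.** Menstrual blood seen at a speculum examination is one observation with two instructions. Under the genitourinary paragraph it is not an AE. Under Table 3 and the one-level rule it is a Grade 1 finding, and a reportable change if baseline was Grade 0. Sites could reasonably follow either.

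The findings table is a separate matter. Even if every site applies the exemption to AE reporting, nothing removes menstrual bleeding from the Grade 1 counts in Table 14.3.5.9. Bleeding is one of five graded local findings for a vaginal gel, and this single-arm trial has no control group against which to judge the background. The bleeding row would then partly reflect where in the cycle the visit happened to fall.

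The baseline raises the opposite difficulty. If the enrollment examination is done during menses and bleeding is graded Present, the item is already at its top level.

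**Working it through.** The plan states no figure on this point, so there is nothing to reproduce. The check is a comparison of rules, followed by an illustration of size.

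**1. What each rule does with expected menstrual blood at an examination**

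| Place | Result |
|---|---|
| Protocol 5.4.3, genitourinary paragraph | Not an AE |
| Protocol Table 3 / SAP 5.1 | Grade 1 |
| Protocol 5.4.3 examination rule, 5.1.3, 5.1.4 | Reportable change if baseline was Grade 0 |
| SAP 4.8.6, Table 14.3.5.9 | Counted as Grade 1 at that visit |

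No cross-reference links the first row to the other three.

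**2. The two-level grade against the one-grade-increase rule**

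| Baseline | Follow-up | Increase of at least 1? |
|---|---|---|
| 0 | 0 | No |
| 0 | 1 | Yes |
| 1 | 0 | No |
| 1 | 1 | No |

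Only 0 to 1 qualifies. A baseline of Present therefore rules out any later increase on this row.

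**3. Illustrative frequency for Visits 3 and 4**

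Assumptions not in the documents: menses last m = 3 to 7 days, the cycle is L = 28 days, and visit days are uniform over the cycle and independent of each other. The chance that one examination falls in menses is p = m/L. The chance for at least one of Visits 3 and 4 is 1 − (1 − p)².

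| m / L | p | At least one of two |
|---|---|---|
| 3/28 | 10.7% | 20.3% |
| 5/28 | 17.9% | 32.5% |
| 7/28 | 25.0% | 43.8% |

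Letting L run over the 21 to 35 days that the plan accepts for an evaluable cycle widens the range: 3/35 = 8.6% to 7/21 = 33.3% per examination, and 16.4% to 55.6% for at least one of the two. If half of the in-menses visits on a 28-day cycle were moved, p would be about 5% to 13% (10.7/2 and 25.0/2).

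**4. Where this illustration does not apply**

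- *Visit 5* is fixed at 14 to 30 days after the seventh study cycle, so it is not uniform over a cycle.
- *Visit 2* carries a gate. Under Protocol 5.1.2, a dipstick of 1+ or more for blood means that the woman is not enrolled at that visit. Menstrual blood in the sample could trigger this, although the clean-catch collection in Protocol 4.7 limits it. Baselines in menses are therefore probably fewer than m/L. The documents do not allow a figure.

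**The case against.** The strongest reply is that the protocol already settles the matter. The exemption stands in the same section, immediately before the examination rule. Footnote n agrees with it. Protocol 5.4.2 defines an AE as an unfavorable and unintended sign, which ordinary menses is not. Footnote g, 5.1.3 and 5.1.4 all bring in the Investigator's judgement. Table 3 concerns vulvar, vaginal or cervical signs and lists bleeding beside petechiae and sloughing, so it can be read as bleeding from those tissues only.

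Much of this stands for AE counts. A reader might infer that the plan turns ordinary menses into AEs with no exemption at all; the documents do not support that. But the exemption sits under a heading that opens with eDiary collection. The Investigator's judgement is tied in 5.1.3 and 5.1.4 to a mechanical one-level rise. The tissue-only reading is plausible but not written down, and none of these points reaches the by-grade summary in SAP 4.8.6.

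A reader might also infer that true gel-related bleeding is hidden in women enrolled during menses. That goes too far. Unexpected bleeding is an AE under 5.4.3 without any grade increase, vaginal bleeding is recorded in the eDiary, and a later Grade 1 still appears in Table 14.3.5.9 whatever the baseline was. What is lost is only the ability to show a rise on this row.

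Finally, the frequencies rest on assumption. Menses length and visit timing come from no document, and the Cycle 0 note shows that enrollment at the onset of menses is foreseen, not how often it happens.

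**Conclusion.** The point holds as a reconciliation of safety rules. The exemption for expected menstrual bleeding is not carried into Protocol Table 3, the examination rule in 5.4.3, Protocol 5.1.3 and 5.1.4, SAP 5.1 or SAP 4.8.6. Followed as written, menses at an examination, mainly at Visits 3 and 4, can inflate the bleeding row of Table 14.3.5.9, and the AE instructions conflict. A baseline of Present blocks a grade increase on that row but does not prevent capture as an AE.

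Under the 28-day assumptions above, at most about 11–25% of Visit 3 or Visit 4 examinations would fall in menses, and fewer if sites reschedule. It would be tempting to apply the same range to baselines, but the dipstick gate at Visit 2 argues against that.

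This is a minor correction to a descriptive safety table. The primary endpoint, power and sample size are unaffected.

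**What to change.** 1. In Protocol Table 3 and SAP 5.1, change the row label to *Bleeding other than expected menstrual bleeding*.
2. In Protocol 5.1.3, 5.1.4 and the examination paragraph of 5.4.3, cross-refer to the exemption in the genitourinary paragraph, so that one AE rule applies.
3. In SAP 4.8.6, flag examinations dated within a recorded menses and present the bleeding row of Table 14.3.5.9 with and without them. Do not set them to missing: that would discard true lesion bleeding seen during menses.
4. In SAP 4.8.6, state that if the enrollment examination fell in menses, the baseline for the bleeding item is the Screening examination, provided that was not itself in menses. SAP 4.2 already lets a specific section override the general baseline rule, and a gynecological examination is scheduled at Screening.

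The cost is wording in a few places, one derivation and some extra table lines. Menses are already recorded (Protocol 5.6, SAP 4.7.1.2, Listing 16.2.6.1), so no new data are needed.
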